8.2 Secondary objectives

- To evaluate the outcomes in sub-group of patients with renal impairment and diabetes
- To evaluate all-cause mortality in rivaroxaban and apixaban, as compared to warfarin

- Drug utilisation and patient characterization of rivaroxaban, apixaban and warfarin receiving standard and reduced dose in accordance and not in accordance with the label
- Drug utilisation/prescription behaviour and patient characterization following the first Intracranial haemorrhage or Ischaemic Stroke during the study period

9. Research methods

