The validity of a nested case-control (NCC) study that follows the incidence-density based NCC paradigm is equivalent to the corresponding cohort study. NCC is simply described as an efficient person-time sampling strategy to obtain the same results as in a cohort study. In this study, this efficiency gain is quite substantial. It is quite common that daily-dose of these drugs changes during follow-up time. As described in the section 9.3.1.1, the algorithm to be used to ascertain daily dose at one specific time-point (one unit of person-time) is already quite complex. An attempt to classify the daily dose of every single unit of person-time of follow-up for the entire cohort would be not only be time-consuming but also prone to misclassification. The reason is that the algorithm is not entirely automated but requires some fine tuning based on recent prescription history. Thus, using a NCC approach enables us to minimize misclassification using all available information to estimate the daily-dose at the two most important time points: a) at index date (date of the event among cases or random date among controls) and b) at start date.

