9.3 Variables

9.3.1 Exposure definition

Among the source population resulting from the THIN database, we will ascertain three separate/mutually exclusive cohorts of new-users of rivaroxaban, apixaban and warfarin (index drug) using the date of first prescription (start date) among the three study drugs. Index date= event date in the nested case-control analysis.

This study will apply a new-users (initiators) design (Ray 2003) and then further stratify the new users into naïve and non-naïve. A patient is considered eligible as new user of rivaroxaban, apixaban or warfarin if he or she had a first prescription of the respective drug recorded during the enrolment period and never received one prior for that index OAC. Further, naïve users are individuals with no previous recorded use of any OAC in the database before the start date. Non-naïve patients are those with one or more oral anticoagulant prescriptions other than the index drug recorded before the start date.

The study drug will be further stratified to Current, recent, past and non-use specified in [section 9.3.3](#)

Among cases of intracranial haemorrhage or ischemic events during the study period, use of the study drugs after index date (index date=event date in the nested case-control analysis) will also be ascertained within one year after the index date.

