- Healthcare utilization in the year prior to the start date/index date (e.g. GP visits, outpatient visits and hospital admissions where available).
- Use of following medications in the three months before the start date: antiplatelet drugs (low-dose acetylsalicylic acid, clopidogrel, dipyridamole, prasugrel, ticlopidine and ticagrelor), antiarrhythmic drugs, antihypertensive drugs, statins, anti-diabetic agents, non-steroidal anti-inflammatory drugs, oral steroids, acid-suppressive drugs, disease-modifying anti-rheumatic drugs, antidepressants, antipsychotic drugs, oral contraceptives, hormone-replacement therapy, strong inhibitors of either cytochrome P450 3A4 or P-glycoprotein (e.g. the systemic azole antimycotics ketoconazole, itraconazole, voriconazole and posaconazole and the HIV-protease inhibitor ritonavir), strong CYP3A4 inducers (e.g. rifampicin, phenytoin, carbamazepine or phenobarbital) and fluconazole.
- Recency of use of medications listed above as well as study drugs on index date will be categorized as:
 - Current use (when the drug supply lasts until index date or supply ends in the 30 days before index date)
 - Recent use (when the drug supply ends 30-90 days before index date)
 - Past use (when the drug supply ends 91-365 days before index date)
 - Non-use: no use in year before index date

Note that for medications other than study drugs, recent and past will be collapsed into one category

- Duration of use will be defined among current users of study drugs at index date as the time from the first consecutive prescription of that drug to index date. Consecutive prescriptions will be considered those separated by a gap of less than 30 days between end of supply and the date of the next prescription. Duration of use will be classified as: up to 90 days, 91 days up to one year, 1-3 years, more than 3 years. Furthermore, these individuals (i.e. current users of study drugs at index date) will be classified as “Continuers” if the first consecutive prescription corresponds to the patient’s start date (i.e. the patient maintained the same drug initiated at start date up until the index date), or “Discontinuers/Switchers” if the patient was not continuously taking the starting OAC between start and index date (i.e. either the patient has interrupted the drug at some point or the patient switched from one OAC to another).

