9.7 Data Analysis

We will first describe the three cohorts according baseline characteristics, use of medications, comorbidities and healthcare utilization services (see variables in section 9.3). This analysis will be based on descriptive statistics: frequencies and percentages will be calculated to the variables of interests, continuous and count variables will be described using mean (\pm standard deviation), proportions, median (quartiles) and minimum and maximum values. 95% confidence intervals will be computed for descriptive variables.

Two independent follow-ups will be performed, one for each analysis. **Safety and effectiveness:** In this follow-up members of all three study cohorts will be followed from the day after start date up until the earliest of: a) first occurrence of Intracranial hemorrhage (intracerebral hemorrhage, subarachnoid hemorrhage, subdural and epidural hematoma), b) an ischemic event (Ischaemic Stroke /Systemic Embolism), c) Myocardial Infarction, d) death, and e) end of study period. **All-cause Mortality:** the follow-up of members of all three study cohorts will be followed from the day after start date up until the earliest of: a) date of death, and b) end of study period. The end of study period is defined as end of last data collection in each practice.

We will then analyze safety, effectiveness, and all-cause mortality associated to use of the study drugs in three independent nested-case control analyses. These three analyses will include all cases identified in each follow-up (respectively: intracranial hemorrhage events, ischemic events, and deaths) and an analysis-specific group of controls. These control groups will comprise a random sample of members of all three cohorts, frequency-matched by age, sex and calendar year to each set of cases ([Walker 1991](#)). Briefly, each cohort member is assigned a random date within the study period. We will consider “eligible controls” all those individuals who are being followed at the time of the random date (e.g. random date included between their start of follow-up and end of follow-up). This process (similar to incidence density sampling) ensures that the likelihood of being selected as control is proportional to the amount of person-time contributed by each patient: as an example a person who contributes all the time included between beginning of study period and end of study period has a 100% likelihood of being an eligible control. Then we will sample “eligible

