controls” in such a way that the frequency of matching factors (age categories, sex, and calendar year) among selected controls at their random dates matches that of the cases at the index date (i.e. frequency-matched controls). In other words, if 2% of cases are males, belong to the age category 40-49 and have 2010 as year of their index date, then 2% of controls are males, belong to the age category 40-49 and have 2010 as year of their random date. Under our study design of incidence density sampling, the odds ratio (OR) is an unbiased estimator of the incidence rate ratio (RR) (Rothman 2012). Unconditional logistic regression models will be used to obtain OR estimates of OAC use adjusted by baseline variables described above and OAC use at index date. The model will include all covariates described in section 9.3.3 in the logistic regression model (fully-adjusted model). Additionally, and depending on the number of cases ascertained, we could explore simpler models based on either change-in-estimate or statistical significance approaches. Specifically the following analyses will be performed for each outcome:

- a) OAC daily dose: We will use the daily dose criteria described in 9.3.1.2 to classify current users of rivaroxaban and apixaban and compare with warfarin as follows:

Rivaroxaban

- Overall Rivaroxaban (both doses) vs warfarin
 - o 20mg OD – No dose reduc. criteria – Appropriate vs warfarin
 - o 20mg OD – Dose reduction criteria – Inappropriate vs warfarin
 - o 15mg OD - No dose reduc. criteria – Inappropriate vs warfarin
 - o 15mg OD – Dose reduction criteria – Appropriate vs warfarin
 - o Overall Appropriate use vs warfarin

Apixaban

- o Overall Apixaban (both doses) vs warfarin
 - 5mg Bid - No dose reduc. criteria – Appropriate vs warfarin
 - o 5mg Bid – Dose reduction criteria – Inappropriate vs warfarin
 - o 2.5mg Bid - No dose reduc. criteria – Inappropriate vs warfarin
 - o 2.5mg Bid – Dose reduction criteria – Appropriate vs warfarin
 - o Overall Appropriate use vs warfarin
- b) Outcomes will also be analysed in the sub-group of diabetes and by renal function (CKD-EPI) (creatinine clearance or serum creatinine as described in the label of the respective NOAC). Since renal function is taken into account in this classification, individuals without

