9.9 Limitations of the research methods

- Given the nature of real-world data, missing data are likely to be present in a minority of instances. As a general strategy, no data imputation strategies will be applied to supplement missing data. However, missing values may occur in a small proportion. In this case, individuals with missing values will be kept in the analysis and a separate category will be created for missing values of that variable.
- Only prescriptions captured in THIN dataset will be available. Medications prescribed at hospital will not be captured nor will over the counter medications (OTC). This might induce some exposure misclassification that we expect to be non-differential. This might introduce to some bias towards the null in study estimates. While bias towards the null is generally considered as conservative in effectiveness analyses, it is considered as anticonservative in safety analyses (tends to conclude treatment strategies are similar even if they are not). We should take this into account when interpreting study results.
- Incomplete data concerning medication compliance: drug use is based on prescriptions written by the treating physician, but no information is available to confirm if the drug was actually taken by the patient (common to virtually any computerized clinical database).
- There may be some missing data if GPs may not enter the hospitalization data however we expect that the vast majority of GPs will record information on hospitalization into THIN.
- Some lifestyle variables such as smoking, BMI and alcohol consumption is not consistently recorded for all patients.
- The results from observational analyses should be interpreted with care, as in the presence of remaining confounding, any findings cannot simply be attributed to use of study drugs.

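### All-cause mortality is analysed only by drug and dose in current use at the date of death, so prescribing changes during final decline can pass for a drug or dose effect

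*Protocol*

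**What the plan says.** Section 8.2 sets a secondary objective: "To evaluate all-cause mortality in rivaroxaban and apixaban, as compared to warfarin". Section 9.7 assigns it a design: "We will then analyze safety, effectiveness, and all-cause mortality associated to use of the study drugs in three independent nested-case control analyses".

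The exposure date follows from three places. Section 9.3.1 has "Index date= event date in the nested case-control analysis". Section 9.1 places dose ascertainment "at index date (date of the event among cases or random date among controls"). Section 9.3.3 defines "Current use (when the drug supply lasts until index date or supply ends in the 30 days before index date"). For a death, exposure is therefore fixed at the date of death with a 30-day carry-over; for a control, at a random date. Under 9.3.1.1, dose at index date comes from the prescriptions before it, with no lag.

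Section 9.7 then says "Specifically the following analyses will be performed for each outcome". The list covers dose and appropriateness contrasts of current rivaroxaban and apixaban users against current warfarin use, and duration contrasts against non-use. Dose is also estimated at start date (9.1 names "the two most important time points: a) at index date (date of the event among cases or random date among controls) and b) at start"), but no listed mortality contrast uses the drug or dose that was initiated.

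Two further statements matter. Section 9.9 says "Medications prescribed at hospital will not be captured" and expects the resulting misclassification to be non-differential, with no exception for deaths. In 9.7 the mortality follow-up ends only at death or the end of data, so an intracranial haemorrhage, stroke or infarction does not end it. The same section hypothesises that anticoagulation restarts one to three months after an event.

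**The concern.** Haemorrhage, stroke and infarction are acute, so exposure on the day is a sensible choice for them. Death from any cause can end a decline that itself changes prescribing: the anticoagulant may be stopped, its dose altered, or the patient admitted and supplied where the database does not see it. Once recorded supply plus 30 days has run out, the death no longer counts as current use. Controls are dated at random and are not selected for closeness to death.

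The protocol supplies two of these mechanisms itself: hospital prescribing goes unrecorded, and a gap of one to three months is expected after events that can be fatal and that leave the patient in mortality follow-up. If haemorrhage or stroke rates differ by drug, which is what the study asks, that second loss would differ by drug too. Supply is also estimated by different rules for warfarin and the NOACs (9.3.1.1), so current status may lapse at different speeds.

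At stake is the mortality comparison with warfarin, and above all its small dose and appropriateness cells.

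**Working it through.** **1. The protocol's own figures (9.5).** Three cohorts of 10,000 at 4% a year give 30,000 × 0.04 × 3 = 3,600 deaths, as stated. The three years are inferred; the same multiplier gives the stated 900 and 1,800 at 1% and 2%. With 50% continuing, current use of one drug among controls is 10,000 × 0.5 / 30,000 = 1/6. With one control per case (the ratio is not stated), power to detect an odds ratio of 1.2 for death is 0.84, in line with the stated figure of over 80%. The power section therefore also rests on index-date exposure, deaths included.

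**2. NOAC versus current warfarin, no true effect.** Let n and w be the shares of NOAC and warfarin deaths that lost current status in excess of controls on the same drug. Among deaths the two current-use cells shrink by (1−n) and (1−w); among controls they do not. Hence OR = (1−n)/(1−w). The protocol gives no values, so these are assumptions:

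| n (NOAC) | w (warfarin) | OR |
|---|---|---|
| 10% | 10% | 0.90/0.90 = 1.00 |
| 20% | 10% | 0.80/0.90 = 0.89 |
| 10% | 20% | 0.90/0.80 = 1.125, given as 1.12 |
| 10% | 25% | 0.90/0.75 = 1.20 |

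Only the excess counts. If 25% of NOAC deaths and 15% of warfarin deaths are non-current, and the same-drug controls show the same 25% and 15%, the OR is 1.00, not 0.75/0.85 = 0.88.

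**3. Dose cells.** Section 9.5 supposes that 30% of current apixaban users take the reduced dose, half of them appropriately: 15% inappropriate reduced and 70% standard. Suppose a share x of standard-dose deaths was moved to the reduced dose before death without meeting the 9.3.1.2 criteria. Against warfarin, with no true effect, OR = (0.15 + 0.70x)/0.15:

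- x = 2%: 0.164/0.15 = 1.09
- x = 5%: 0.185/0.15 = 1.23
- x = 10%: 0.220/0.15 = 1.47
- x = 12.9%: 0.240/0.15 = 1.60, the detectable OR that 9.5 gives for this contrast and outcome

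The standard-dose OR moves the other way, to 1 − x (0.95 at x = 5%).

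**4. Current use versus non-use (duration analysis).** Non-use means no use in the year before, so late withdrawals fall into recent or past use and only the current cell shrinks: OR = 1 − w, or 0.90 and 0.80 at 10% and 20%.

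**5. Benchmark for step 2.** The 1.2 in 9.5 is for current use of each drug, reproduced above as one drug against everyone else. For current NOAC against current warfarin, a third of the 3,600 deaths (1,200) enter the contrast, and the detectable OR at 80% power is about 1.26 with one control per case and 1.20 with four.

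**The case against.** Much can be said for the plan. The main contrast uses an active comparator, so withdrawal common to both drugs cancels exactly. The 30-day carry-over absorbs short final gaps and short admissions. The full model adjusts for the frailty index, cancer, other comorbidity and admissions in the prior year, whereas the odds ratios above are crude. A dose change that follows worsening creatinine or weight may meet 9.3.1.2 and go to the appropriate cell. Start-date exposure answers a question about initiation, not treatment; with 9.5's 50% continuation scenario it could be heavily diluted. Mortality is secondary, and an analysis plan not shown here could add sensitivity analyses.

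Most of this stands, and it limits the size of the problem. It does not remove it. Equal excess loss across drugs is an assumption the protocol neither states nor supports. One-way dose changes outside the listed criteria do not cancel. Adjustment cannot restore an exposure that approaching death has already altered. Nor is this a detail left to the analysis plan: the protocol itself fixes index-date exposure for deaths, and an analysis plan that follows it would do the same.

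**Conclusion.** The point holds as a weakness in a stated design choice for a secondary outcome. Moderate assumed differences in terminal withdrawal (10% against 20%) move a null NOAC versus warfarin odds ratio to 0.89 or 1.12, and an assumed 5% one-way dose shift moves the inappropriate reduced apixaban cell to 1.23. All these shares are assumptions, the direction is unknown, and carry-over and adjustment would shrink the effect.

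A reader might infer more than the document supports:

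- That the mortality result is certain to be biased. It is not: equal excess loss gives 1.00, and if withdrawal is equal across drugs and doses and no dose is changed, the dose cells are unbiased against warfarin too.
- That any difference in the raw share of deaths off treatment is bias. Ordinary discontinuation also occurs in controls and drops out.
- That a spurious 1.2 for NOAC versus warfarin equals the protocol's detectable effect. That figure belongs to a different contrast (step 5).
- That start-date exposure must replace current use as the main mortality analysis. That is a debatable choice between two questions, and the document does not settle it.

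The haemorrhage and ischaemic analyses are not affected by this point.

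**What to change.** In 9.7, for all-cause mortality only, pre-specify an additional contrast by drug and dose at start date, reported beside the current-use result. State that the mortality conclusion will be qualified if the two disagree. In 9.9, add that the non-differential expectation may not hold for deaths, because people who die are more likely than controls at a random date to have been in hospital shortly before.

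The cost is protocol wording and one further set of models. Drug and dose at start date are already ascertained for cases and controls, and this contrast matches the initiator cohorts in 9.3.1 and the objective in 8.2. Its weakness is dilution when patients stop or switch, so it supplements the current-use analysis and does not replace it.

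Optionally, add an analysis with exposure lagged 90 days in cases and controls alike, restricted to people with at least 90 days of follow-up. This costs more: 9.1 plans dose at two time points only and says the algorithm is not fully automated, so dose and label-criteria status would have to be derived at a third.

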Bayer has recently conducted a retrospective cohort study on prescription patterns of NOACs in NVAF patients in UK general practice using a combination of the THIN and CPRD databases. Amongst patients without an apparent indication for dose reduction, the reduced dose was prescribed in approximately 30% of patients receiving apixaban and 10% of patients receiving rivaroxaban in the new-users of both agents (Study 19330, unpublished data). We therefore hypothesize that in the UK, the higher than expected rates of reduced dose apixaban use as compared to the Phase III trials will exhibit higher rates of stroke and systemic embolism versus warfarin than rivaroxaban, which appears to be prescribed at the reduced dose less frequently. Also, patients with renal impairment receiving standard dose are at increased risk of bleeding. Although, warfarin use has certainly decreased in the recent years, this drug remains the main oral anticoagulant used in the UK. It has also been the active comparator of choice in most clinical trials of NOAC (O'Dell et al.) and in our opinion constitutes an ideal reference drug for these analyses. Both the standard and the reduced dose of NOACs have been compared to warfarin in clinical trials and shown to be as safe and effective as warfarin. Warfarin itself does not have dose-reduction requirements however the dose needs to be adjusted to maintain INR between 2.0-3.0. Rivaroxaban and apixaban are most widely used NOACs in the UK whereas the use of dabigatran is low and declining since 2014 (Study 19330, unpublished data). Also, the appropriate and inappropriate use of dabigatran is difficult to estimate due to a multiple criterion in the label for dose reduction which is difficult to assess using secondary data sources. Risk of major bleeding especially GI bleeding for NOACs is extensively studied, and our research question is to study the effect of under-dosing on the risk of stroke (effectiveness outcome). However, to also study the other side of the balance which is bleeding, we included ICH because it is an event comparable to stroke in terms severity. GI bleeding is an acute event, usually followed by complete recovery in vast majority of patients. In terms of the balanced outcomes, it is important to take account of the severity of the disease events prevented and caused by the intervention, and not just the frequencies of the events. Thus GI bleeds, which are sometimes severe, are acute events usually followed by recovery without sequelae, while strokes and ICH can leave residual physical and/or cognitive impairments in those who survive, and may require complex and lifelong interventions. Therefore, GI Bleeding is not included as an outcome in this study.

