9.2.2 Study time frame

The study period extends from 1st January 2012 up to last available database extraction (at time of writing, December 2017). Rivaroxaban was first marketed in 2008 in the UK, whereas apixaban was introduced in 2011. By choosing this study period we ensure that all three study drugs were available throughout the study.

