9.3.3 Covariate definition

The following variables will be collected among the three study cohorts (apixaban, rivaroxaban and warfarin) both at start and index date (the date among cases and controls):

- Age and sex distribution at start date/index date
- Naïve/Non-Naïve at index date: Use of OAC other than the index OAC before index date
- Frailty: we will estimate an electronic frailty index (eFI) at start date/index date by using an algorithm developed and validated in THIN (Clegg et al. 2016). Briefly the eFI score is simply an equally weighted calculation of deficits present out of the total 36 deficits identified. Patients will be classified into four mutually exclusive categories based on this score: a) Fit = 0-0.12, b) Mild frailty = 0.12-0.24, c) Moderate frailty = 0.24-0.36, and d) Severe frailty = >0.36.
- Renal disease: estimated glomerular filtration rate (eGFR) before start date/index date will be calculated using the formula described in Table S1 (Annex 3). In prior studies we found that eGFR could not be estimated in less than 5% of AF patients. ACR (Albumin/Creatinine Ratio) will also be ascertained.
- Comorbidity: history of haemorrhagic disease and history of intracranial haemorrhage, urogenital bleeding and gastrointestinal bleeding. Liver disease, pancreatic disease, cancer, cardiovascular disease (acute MI, coronary artery disease, congestive heart failure, ventricular arrhythmia, peripheral arterial disease) cardiovascular risk factors (hypertension, diabetes mellitus, hyperlipidaemia and obesity), stroke/TIA, respiratory disease (asthma and chronic obstructive pulmonary disease), rheumatoid arthritis, osteoarthritis, gastrointestinal disease, liver disease and pancreatic, alcohol-related disorders before start date/index date.
- CHADS2 (0-6) and CHA₂DS₂Vasc (0-9) scores will be calculated at start and index date based on the presence/ history of congestive heart failure, hypertension, age, diabetes mellitus and prior stroke or transient ischaemic attack. HAS-BLED (0-9) score for major bleeding risk (hypertension, renal disease, liver disease, stroke history, prior major bleeding or predisposition to bleeding, age > 65, medication usage predisposing to bleeding, alcohol usage history), will also be calculated. Numbers and proportion will be calculated per value.
- Smoking status, body mass index (BMI) and Townsend score: most recently recorded value before the start date/index date.

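### Controls are matched on calendar year, but the fully-adjusted model leaves calendar year out, so the NOAC-versus-warfarin odds ratios are biased, usually toward 1

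*Protocol*

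**What the plan says.** Under protocol section 9.7 the controls are a random sample of the three cohorts, "frequency-matched by age, sex and calendar year to each set of cases". They are drawn so that the "frequency of matching factors (age categories, sex, and calendar year) among selected controls at their random dates matches that of the cases". The match therefore equalises the joint distribution of all three factors between cases and controls.

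The analysis does not condition on matched sets: "Unconditional logistic regression models will be used to obtain OR estimates of OAC use adjusted by baseline variables described above and OAC use at index". Next it names the adjustment set: "The model will include all covariates described in section 9.3.3 in the logistic regression model (fully-adjusted model". The first entry in section 9.3.3 is "Age and sex distribution at start date/index date". The rest covers naïve status, frailty, renal function, comorbidity, risk scores, lifestyle, healthcare use, co-medication, recency and duration. Calendar year does not appear there, in the abstract's account of the analysis, or elsewhere as a model term.

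Section 9.7 then allows simpler models chosen by change-in-estimate or statistical significance, and protects no term from removal. It also states that under this design "the odds ratio (OR) is an unbiased estimator of the incidence rate ratio (RR").

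On exposure over time, section 7 says: "Although, warfarin use has certainly decreased in the recent years, this drug remains the main oral anticoagulant used in the UK". Section 9.2.2 sets the span: "The study period extends from 1st January 2012 up to last available database extraction (at time of writing, December 2017").

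**The concern.** Matching controls to cases on a factor changes the exposure mix of the controls. If the factor predicts exposure, the controls no longer show the exposure prevalence of the person-time that produced the cases. The sampling argument for reading the odds ratio as a rate ratio then holds only within levels of that factor. Two of the three matching factors return to the model through 9.3.3. The third does not, and it is the one tied to the choice between warfarin and a NOAC in 2012–2017.

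Warfarin is the reference for every daily-dose comparison in 9.7, so the primary safety and effectiveness estimates are all exposed to this. Section 9.9 itself notes that bias toward the null is anticonservative in a safety analysis. The reduced-model option adds a second risk. Frequency matching removes the marginal association of the matching factors with case status, so a significance rule could drop age and sex as well.

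**Working it through.** The protocol gives no figure for this bias. Section 9.5 supplies a yardstick for precision. Its event counts reproduce as 30,000 patients × 1%, 2% or 4% a year × 3 years = 900, 1,800 and 3,600; the 3 years are implied, not stated. For intracranial haemorrhage it claims more than 80% power at an odds ratio of 1.5, two-sided 5%. At exactly 80% power the standard error of the log odds ratio is ln(1.5)/(1.96 + 0.84) = 0.405/2.80 = 0.145; higher power means a smaller standard error.

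**One NOAC group against warfarin**

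- p_y = NOAC share among controls in year y (assumed).
- Share among cases: q_y = OR·p_y / (1 − p_y + OR·p_y).
- Matching gives cases and controls the same year weights w_y.
- Odds ratio when year is ignored: [Σw_y q_y / (1 − Σw_y q_y)] ÷ [Σw_y p_y / (1 − Σw_y p_y)].

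Worked case, true OR 1.5, equal weights over six years:

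- p = 0.05, 0.12, 0.22, 0.35, 0.48, 0.60; mean 0.3033.
- q = 0.0732, 0.1698, 0.2973, 0.4468, 0.5806, 0.6923; mean 0.3767.
- Pooled OR = (0.3767/0.6233) ÷ (0.3033/0.6967) = 0.6044/0.4353 = **1.39**.

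The year-specific odds ratio is 1.5 in each of the six years.

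For the ranges, cases by year were set proportional to person-time × baseline rate × (1 − p_y + OR·p_y). Person-time was either flat or rising 1 to 6, and the baseline rate trended by −10%, 0 or +10% a year.

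| Assumed NOAC share, 2012 to 2017 | True 0.5 | True 1.0 | True 1.5 |
|---|---|---|---|
| 20% to 50%, linear | 0.51 | 1.00 | 1.47–1.48 |
| 5% to 60%, as worked above | 0.54–0.56 | 1.00 | 1.39–1.43 |
| 3% to 80% (0.03, 0.10, 0.25, 0.45, 0.65, 0.80) | 0.59–0.62 | 1.00 | 1.30–1.36 |

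Against the standard error of 0.145, a shift from 1.5 to 1.48 is ln(1.5/1.48)/0.145 = 0.1 standard errors. A shift to 1.39 is 0.5, and to 1.30 about 1.0.

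**Rivaroxaban and apixaban in one model**

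Assumed control shares by year are rivaroxaban 0.03, 0.10, 0.18, 0.25, 0.30, 0.32 and apixaban 0, 0.03, 0.10, 0.20, 0.30, 0.40. Take true rivaroxaban 1.0 and apixaban 1.5, with equal case counts by year:

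- Cases: warfarin 0.5990, rivaroxaban 0.1758, apixaban 0.2252.
- Controls: 0.6317, 0.1967, 0.1717.
- Rivaroxaban OR = (0.1758/0.5990) ÷ (0.1967/0.6317) = 0.2935/0.3114 = **0.94**.

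With equal or rising case counts:

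| True rivaroxaban / apixaban | Rivaroxaban without year | Apixaban without year |
|---|---|---|
| 1.5 / 1.5 | 1.36–1.40 | 1.32–1.37 |
| 1.0 / 1.5 | 0.94–0.96 | 1.38–1.41 |
| 0.9 / 1.5 | 0.86 | 1.40–1.42 |
| 1.1 / 0.6 | 1.14–1.15 | 0.63–0.64 |

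In the last three rows rivaroxaban moves away from 1.

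**Does adding year repair it?** An unconditional logistic fit to 400,000 simulated cases and 400,000 controls, with these shares, rising case counts and true odds ratios of 1.5 for both drugs, gave 1.40 (rivaroxaban) and 1.37 (apixaban) without year indicators. With them it gave 1.50 and 1.51.

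**The case against.** **The text is inclusive.** Section 9.7 says which covariates go in; it does not say that nothing else does. The sentence before refers to baseline variables described above, in a section that names the matching factors. Entering matching factors in an unconditional model is also routine detail for an analysis plan, which is not shown here. It is fair that no sentence excludes year, and an experienced analyst might add it. But the protocol is not silent: it names the fully-adjusted set by reference to a list that holds two matching factors and lacks the third. An analysis that follows it as written carries the bias.

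**The size is unknown.** This stands. The protocol gives no yearly shares, and its one statement on level is that warfarin remained the main oral anticoagulant in the UK. That concerns overall use, not this new-user cohort, but it keeps the mild pattern in play, where the bias is about 2%. Duration of use, which is in 9.3.3, may partly stand in for calendar time.

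**Against the study's precision the shift is modest.** In the illustrations it is 0.1 to 1.0 standard errors for intracranial haemorrhage. It does not reverse a two-group result or create a false positive there.

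**A tempting stronger reading** is that every NOAC-versus-warfarin odds ratio is pulled toward 1. The documents do not support it. In a two-group comparison a true odds ratio of 1 stays at 1.00, and 9.7 plans several rivaroxaban and apixaban categories against one warfarin reference, where one category's effect can push another away from 1.

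**Conclusion.** The point holds. The adjustment set written into 9.7 omits a factor on which the controls are matched and which, by the protocol's own account, is related to exposure. For that model the unbiasedness statement is not true. The bias is usually toward 1. Away-from-1 movement is possible for a category near 1 when another category has a clear effect; with true values of 1.0 and 1.5, rivaroxaban would appear at 0.94–0.96.

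The magnitudes are illustrations, not estimates. They rest on assumed yearly drug shares, person-time and event-rate trends, a year-constant odds ratio and no other covariates. Across the patterns shown, a true 1.5 is reported as anything from 1.48 down to 1.30. The direction of the remedy depends on none of these figures, and the primary comparisons are affected, so the text should be corrected before analysis.

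**What to change.** Add to section 9.7 that every logistic model (full, reduced, subgroup, and naïve or non-naïve) includes age category, sex and calendar year of the index or random date as forced terms, preferably as the joint strata used for matching. State that neither change-in-estimate nor significance-based selection may remove them. Word the unbiasedness statement as applying to models that contain the matching factors.

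The cost is a sentence or two of text and a few model terms. The index or random date already exists for every case and control, so no new data or sampling is needed. If joint strata are too sparse in the smaller subgroups, separate terms for age category, sex and year can be used there, with that choice stated in advance.
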